APPENDIX B

EORTC-QLQ-C30 (version 3) appended

ENGLISH

EORTC QLQ-C30 (version 3)

We are interested in some things about you and your health. Please answer all of the questions yourself by circling the number that best applies to you. There are no "right" or "wrong" answers. The information that you provide will remain strictly confidential.

Please fill in your initials: **aaaa**
 Your birthdate (Day, Month, Year): **bdbdbccd**
 Today's date (Day, Month, Year): 31 **bdbdbccd**

	Not at All	A Little	Quite a Bit	Very Much
1. Do you have any trouble doing strenuous activities, like carrying a heavy shopping bag or a suitcase?	1	2	3	4
2. Do you have any trouble taking a long walk?	1	2	3	4
3. Do you have any trouble taking a short walk outside of the house?	1	2	3	4
4. Do you need to stay in bed or a chair during the day?	1	2	3	4
5. Do you need help with eating, dressing, washing yourself or using the toilet?	1	2	3	4

During the past week:

	Not at All	A Little	Quite a Bit	Very Much
6. Were you limited in doing either your work or other daily activities?	1	2	3	4
7. Were you limited in pursuing your hobbies or other leisure time activities?	1	2	3	4
8. Were you short of breath?	1	2	3	4
9. Have you had pain?	1	2	3	4
10. Did you need to rest?	1	2	3	4
11. Have you had trouble sleeping?	1	2	3	4
12. Have you felt weak?	1	2	3	4
13. Have you lacked appetite?	1	2	3	4
14. Have you felt nauseated?	1	2	3	4
15. Have you vomited?	1	2	3	4
16. Have you been constipated?	1	2	3	4

Please go on to the next page

ENGLISH

During the past week:

	Not at All	A Little	Quite a Bit	Very Much
17. Have you had diarrhea?	1	2	3	4
18. Were you tired?	1	2	3	4
19. Did pain interfere with your daily activities?	1	2	3	4
20. Have you had difficulty in concentrating on things, like reading a newspaper or watching television?	1	2	3	4
21. Did you feel tense?	1	2	3	4
22. Did you worry?	1	2	3	4
23. Did you feel irritable?	1	2	3	4
24. Did you feel depressed?	1	2	3	4
25. Have you had difficulty remembering things?	1	2	3	4
26. Has your physical condition or medical treatment interfered with your family life?	1	2	3	4
27. Has your physical condition or medical treatment interfered with your social activities?	1	2	3	4
28. Has your physical condition or medical treatment caused you financial difficulties?	1	2	3	4

For the following questions please circle the number between 1 and 7 that best applies to you

29. How would you rate your overall health during the past week?

New agents that control disease progression—while improving tumor-related symptoms, rather than causing significant therapy related morbidity—are vitally needed to treat patients with advanced cancer, including those with colorectal cancer. An approach has been taken to develop such an agent using a monoclonal antibody to block the chronic inflammation involved in both malignant disease progression and constitutional symptoms.

Xilonix™ is expected to inhibit tumor growth and metastasis by interrupting crucial signals that drive angiogenesis and invasiveness. The antibody therapy may also block tumor microenvironment infiltration by leukocytes (such as myeloid suppressor cells) that suppress antitumor immunity, enabling better host immune control of the disease. In addition to local effects on the tumor, Xilonix™ is expected to work systemically to correct the metabolic dysregulation, fatigue and anxiety mediated by chronic inflammatory signaling to the central nervous system. The use of this antibody monotherapy to target chronic inflammation is proposed as a safe, effective treatment for patients with metastatic colorectal cancer.

2 Study Design

This is a phase III, multicenter, double blind, randomized, placebo controlled pivotal trial of the True Human monoclonal antibody MABp1 in subjects with metastatic colorectal cancer who are refractory to standard therapy.

- Enrolled subjects will be randomized (2:1) to receive either MABp1 plus best supportive care (BSC) or placebo plus BSC.
- BSC is defined as those measures intended to provide palliation of symptoms and improve quality of life. This includes, but is not limited to, antibiotics, anti-emetics, narcotics, and parenteral nutrition.
- Subjects randomized to MABp1 or placebo will receive the study drug via intravenous infusion once every 2 weeks (one cycle).

3 Study Endpoints:

3.1 Primary Efficacy Endpoint:

- Overall survival (OS) will be the primary endpoint of this study, survival time will be defined as the duration from the date of randomization until death. Subjects who are alive at the data inclusion cutoff date for the analysis will be censored at that date and survival time will be defined as time from randomization to censor date. Patients lost to follow-up and untraceable for survival status will be censored on the last date subject was known to be alive or lost to follow-up. The overall survival between the Xilonix™ + BSC group and placebo + BSC group will be compared using an unadjusted log-rank test.

3.2 Secondary Efficacy Endpoints:

Secondary efficacy variables will include 1) change in lean body mass (LBM) measured by dual-energy X-ray absorptiometry (DEXA) scans, 2) change in function, symptoms and overall quality of life assessed through the cancer-specific EORTC QLQ-C30¹ questionnaire, 3) change of platelet counts, 4) progression free survival (PFS), 5) objective response rate (ORR) 6) disease control rate (DCR)

The change from baseline on LBM, EORTC score, and platelet count will be calculated by subtracting the baseline (screening) value from that at follow-up (cycle 5 day 1 or off-study visit for patients who completed at least cycle 3 day 1).

Quality of life (QoL) in patients participating in the trial will be evaluated using the European Organization for Research and Treatment of Cancer (EORTC) version 3.0 questionnaire (Appendix). The EORTC QLQ-C30 questionnaire incorporates nine multi-item scales: five functional scales (Physical, Role, Cognitive, Emotional and Social); three symptom scales (Fatigue, Pain and Appetite loss); and a Global Health Status/QoL scale. Each item, excepting Global Health Status, is answered on a four-point scale: “not at all”, “a little”, “quite a bit”, and “very much”. Response to Global Health Status is measured on a 1 to 7 scale, 1 being “very poor” and 7 being “excellent”. Using EORTC specified methodology (Appendix); responses to all the scales will be linearly transformed to reach the scale range 0 to 100.

Immune Related Response Criteria: Tumor response will be assessed by using immune-related response criteria (irRC). The imaging service provider (core laboratory) will acquire images from clinical sites. Review of image data will be conducted in the core lab by qualified and trained radiologists blinded to treatment status. The procedures used for CT/MRI image analysis, reporting of tumor response data and storage and archiving of images will follow the standards laid out in the prospectively determined Imaging Review Charter.

irRC Evaluation:

The detailed evaluation methodology is documented in the Imaging Review Charter. Briefly, for each imaging session, the sum of the products of the two largest perpendicular diameters (SPD) of all index lesions (5 lesions per organ, up to 10 visceral and 5 cutaneous lesions with

a minimum size of $\geq 5 \times 5$ mm) will be calculated. Index lesions will be identified at baseline, and will be followed throughout the patient's participation in this study. At each subsequent imaging assessment, new lesions (defined as a lesion with $> 5 \times 5$ mm measurements) will have their products of diameters measured for use in calculating tumor burden. Tumor burden will be calculated by summing the SPD of target lesions with the SPD of the new measurable lesions.

Table 1: irRC Response Definitions:

Complete Response (irCR):	Disappearance of all lesions in two consecutive observations not less than 4 weeks apart
Partial Response (irPR):	$\geq 50\%$ decrease in tumor burden compared with baseline in two observations at least 4 weeks apart
Stable Disease (irSD):	50% decrease in tumor burden compared with baseline cannot be established nor 25% increase compared with nadir
Progressive Disease (irPD):	At least 25% increase in tumor burden compared with nadir (at any single time point) in two consecutive observations at least 4 weeks apart
Not Evaluable (NE)	Progression has not been documented and one or more index lesions have not been assessed or have been assessed using a different method than baseline that makes comparability impossible.

Table 2: Derivation of irRC Overall Response

Overall lesions response at each assessment			
Index and new lesions (tumor burden), * %	Non-Target Lesions	New Lesions	Overall Response
$\downarrow 100$	Absent	Absent	irCR †
$\downarrow 100$	Stable	Any	irPR †
$\downarrow 100$	Unequivocal progression	Any	irPR †
$\downarrow > 50$	Absent/Stable	Any	irPR †
$\downarrow > 50$	Unequivocal progression	Any	irPR †
$\downarrow < 50$ to $< 25\uparrow$	Absent/Stable	Any	irSD
$\downarrow < 50$ to $< 25\uparrow$	Unequivocal progression	Any	irSD
> 25	Any	Any	irPD †

* Decreases assessed relative to baseline, including measurable lesions only ($\geq 5 \times 5$ mm).

† Assuming response (irCR and irPR) and progression (irPD) are confirmed by a second, consecutive assessment at least 4 weeks apart.

Best overall response (BOR), determined from the sequence of cycle responses assessed, will be used for analyzing ORR and DCR.

Progression Free Survival (PFS): This will be defined as time from randomization to progression of disease or death as defined in Table 1 below, whichever is earlier. Patients surviving without objective disease progression at the end of the data inclusion cutoff date will be censored. If there is no baseline disease progression assessment, then PFS will be censored at randomization. An adequate tumor assessment is defined as a set of radiologic images, which has been transmitted to the central imaging vendor for the purposes of assessing change in tumor measurements according to the immune related response criteria. In order to be considered adequate, the images should include assessment of chest, abdomen and pelvis using the same imaging modality as the baseline scan and should include all target and non-target lesions.

Table 3: Definitions for Assessment of PFS

Situation	Date of Progression or Censoring	Outcome
No baseline assessment	Randomization	Censored
Progression documented between scheduled visits	Next scheduled visit	Progressed
No progression	Date of last visit with adequate assessment	Censored
Investigator claim of clinical progression	Scheduled visit (or next scheduled visit if between visits)	Progressed
Treatment discontinuation for toxicity or other reason	Date of last visit with adequate assessment	Censored
New anticancer treatment started with no claim of progression	Date of last visit with adequate assessment	Censored
Death before first PD assessment	Date of death	Progressed
Death between adequate assessment visits or after patient misses one assessment visit	Date of death	Progressed
Death after an extended lost-to-follow-up time (two or more missed assessments)	Last visit with adequate assessment	Censored

Objective Response Rate (ORR): The ORR will be estimated by dividing the total number of patients with confirmed complete response (CR) and partial response (PR) by the total number of patients in the ITT population.

Disease Control Rate (DCR): The DCR will be estimated by dividing the total number of patients with confirmed CRs, PRs and stable disease (SD) by the total number of patients in the ITT population.

3.3 Exploratory Endpoint:

Clinical Response Rate (CRR) will be the exploratory endpoint for this study. This will be a composite measure assessing the change in LBM, fatigue, pain, and appetite from baseline to week 8. Clinical response will be defined as, 1) Improvement or stabilization (≥ 0 kg change) of LBM as assessed by DEXA scan, and 2) Improvement or no worsening (≤ 0 score point change; low scores reflect better functioning and lower symptom distress) on any two of the three symptom scale measures (fatigue, pain, appetite) of EORTC QLQ-C30. Patients missing the follow-up assessment will be considered non-responders.

3.4 Safety Endpoints:

Safety endpoints will be evaluated by monitoring adverse events from clinical and laboratory reporting. Adverse events will be graded according to the National Cancer Institute Common Terminology Criteria for Adverse Events (NCI-CTCAE, version 4.0). Significant trends in the distribution and severity of the adverse events across the study groups will be assessed.

4 Independent Data Monitoring Committee (IDMC):

An Independent Data Monitoring Committee (IDMC) will be formed to safeguard the interests of trial participants, assess the safety and efficacy of the interventions during the trial, and monitor the overall conduct of the clinical trial. The committee will meet after every 200 subjects enrolled (or 6 months, whichever occurs first) until the first interim analysis to monitor early evidence of treatment harm, and make any appropriate recommendations. After the first interim analysis, the meeting will occur at each subsequent analysis or every year, whichever occurs first. IDMC recommendations will include whether to continue, suspend, or otherwise modify enrolment. Monitoring for early toxicity will be continuous until the first interim analysis, after which this monitoring will occur at each subsequent scheduled interim analysis or every year, whichever occurs first. Full details of the role and responsibilities of the IDMC are described in the IDMC charter.

5 Sample Size and Power

Prior research has reported a median survival of 4.6 months among refractory, metastatic colorectal cancer patients with BSC in a comparable patient cohort. On the other hand, as observed in the colorectal cancer cohort of our phase I/II trial, the median survival was 6.7 months for all enrolled colorectal cancer patients and 8.7 months for the per-protocol population. Using a conservative approach, the current study is designed to detect at least 30% improvement in median OS in treatment arm (6.0 months, hazard rate in treatment arm (h_1)=0.116) compared to the control arm (4.6 month, hazard rate in control arm (h_0)=0.151). We propose to test the null hypothesis for hazard ratio (h_1/h_0)=1 and alternative hazard ratio ≤ 0.767 . A total of 552 deaths will be required to detect the 30% increase in median survival (from 4.6 to 6.0 months, hazard ratio 0.767) with one-sided Type I error probability (α) of 0.025, and 80% power (1-

beta=0.80). With a 2:1 allocation ratio and 5% oversampling, a total of 600 subjects (400 and 200 in treatment and control arm respectively) with 18 month follow-up of the overall study population will provide the required number of events (deaths). The survival curves will be estimated with the Kaplan–Meier method and compared for statistical significance by an unadjusted log-rank test.

5.1 Interim Efficacy Analyses:

Two interim efficacy analyses will be conducted before the final analysis of overall survival. As determined based on alpha spending function of O'Brien and Fleming sequential group design (O'Brien PC, Fleming TR, 1979), survival analyses will be performed after 276 (50%), 414 (75%) and 552 (100%) deaths at the respective stages. After the required number of events for the specific interim analysis has occurred, the database will be frozen for planned statistical analysis.

The criteria for the early termination for efficacy (rejection of null hypothesis) or to accept the null hypothesis will be based on the group sequential design. If the test statistics crosses the pre-specified boundaries for type I error (alpha cut-off 0.0029, 0.0121, and 0.025 at the first, second interim or final analysis respectively) the trial will stop for efficacy. Otherwise the trial continues to the next stage.

The cumulative p value for the acceptance boundary (beta) will be 0.25 and 0.08 at the first and second interim respectively. If efficacy is established at an interim analysis, enrollment will be stopped and the control group will be allowed to crossover. All subjects will be followed up until death, loss to follow-up, or termination of the study. SAS codes for O'Brien and Fleming sequential group design will be included in the Interim Analysis Plan. TFL shells for interim analysis are provided in the Appendix section. The decision rule with interim monitoring will be as follows:

1. If type I error probability (alpha) \leq the above specified cumulative alpha level at the given stage, trial will stop for efficacy
2. Else, if the p value \geq the above specified beta levels the trial will stop for accepting null hypothesis
3. Else the trial will continue to the next stage
4. At final analysis, if alpha is ≤ 0.025 then declare efficacy; otherwise accept the null hypothesis.

The Trial Statistician, who is independent from the study statistician, will conduct these interim analyses as well as the end-of-study final analysis. The Trial Statistician will be responsible for presenting the unblinded interim data to the IDMC. Prior to completion of the trial, unblinded access to the interim efficacy data will only be available to the IDMC for review and the committee has the responsibility of making recommendations to the sponsor based on this data.

6 Randomization Strategy

A central randomization scheme with Interactive Web Response System (IWRS) will be employed to facilitate effective randomization and allocation concealment. The scheme will involve a block randomization technique, randomly assigning participants within blocks based on a 2:1 allocation ratio to the Xilonix™ and placebo arm respectively. After confirmation of eligibility, the study coordinators at the clinical site will complete the randomization eCRF indicating the patient has met inclusion criteria and is ready to be randomized. This step will initiate an IWRS procedure, which will assign the next available sequential randomization number specifying the arm allocation. The randomization sequence will be generated using Oracle Clinical Remote Data Capture (OC RDC) application (Oracle Corporation, Redwood City, CA, USA). The randomization code and the study arm assignment will be maintained inside the RDC system. The randomization will not be stratified on any factor.

7 Statistical Methods

7.1 Analysis Populations:

The primary efficacy analysis will be conducted on an intent-to-treat (ITT) basis. The ITT population will consist of all randomized patients. Patients will be grouped according to treatment group.

Some major changes were made to protocols version V3.0 onwards. Prior to V3.0 this trial was an open label, 1:1 random allocation study where patients received MABp1 (3.75 mg/kg) plus BSC or megestrol acetate plus BSC. Some of the major changes to protocols V3.0 onwards were a double blind placebo controlled design with 2:1 allocation ratio. Dosing regimen also changed from 3.75 mg/kg to 7.5 mg/kg of MABp1. Given the nature of change to the study design patients enrolled on protocols prior to V3.0 modification will not be included in the analysis.

A secondary analysis of the efficacy endpoints will be performed on Per Protocol (PP) patients. The PP population will be defined as those patients in the ITT set who are compliant with the study protocol. Patients will be grouped according to treatment groups.

The Safety analysis will be based on the Safety Population, defined as enrolled patients receiving at least one dose of study drug. Patients will be grouped according to actual treatment received.

7.2 Incomplete Follow-up:

Patients discontinued or lost prior to cycle 3 visit (and therefore not having the second DEXA), or those discontinuing between cycles 3 and 5 but did not complete off-study visit, will not be included for secondary efficacy outcome assessment for absolute change in LBM, or EORTC endpoints.

For the PFS assessment, patients discontinued or lost without evidence of tumor progression will be censored according to Table 1 .

7.3 Missing Data:

Every effort will be made to identify and recover the missing data from the centers. If the data remained missing following such efforts, and contributes 2% or more of total number of patients for the continuous co-variables selected for the Cox model, it will be imputed through multiple imputations (using SAS PROC MI, pooled by PROC MIANALYZE option). Sensitivity analysis will be performed to assess the effect of imputation.

The primary efficacy analysis will be performed using the available data, no imputation will be made. Also the missing data for primary or secondary outcome variables, except for platelet counts, will not be imputed. For platelet counts missing on cycle 5 visit, the available value on cycle 3 or cycle 4 visit will be carried forward. Imputation of missing data will not be carried out for descriptive analyses.

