Another supportive analysis will include a multivariate Cox proportional hazards regression (CPH) method assessing independent predictors of OS after adjusting for potential confounders. Selection of covariates will primarily be based on *a priori* knowledge, and include age (continuous scale), prior cancer therapy (number of regimens will be entered on continuous scale), ECOG performance status (2 categories ECOG 0 and 1 pooled together, and ECOG 2), and KRAS mutation status (coded as no=0, yes=1), and baseline body mass index (BMI). Covariates may be excluded from model if the number of patients representing 1 level of that variable is insufficient. A backward selection method will be used for variable selection; the p-value threshold will be set at 0.10. The proportional-hazard assumption will be tested by Schoenfeld residual analysis. The hazard ratio (HR) and 95% Wald confidence interval (CI) for the HR will be computed and presented in the results. The CPH analysis will be exploratory in nature.

8.4.2 Secondary Effectiveness Endpoints:

LBM: LBM change will be compared across treatment groups both by responder analysis and assessing absolute change.

Patients showing stabilization or improvement from baseline (≥ 0 kg change) will be considered LBM responders and those experiencing LBM reduction will be defined as non-responders. Patients not having a second evaluation for going off the study or any other reason will be considered non-responders. LBM response rate will be compared using Pearson chi-square test. Proportion by group, relative risk and odds ratio estimates will be presented with Cochran-Mantel-Haenszel (CMH) 95% confidence intervals (95% CI).

Absolute change will be compared between treatment groups using an analysis of covariance (ANCOVA) method (SAS GLM procedure) with treatment groups as the factor and baseline value as covariate. The difference in least-square means and 2-sided P values will be derived from the ANCOVA model.

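### The primary survival test is valid but leaves out screening ECOG, forgoing power that a stratified log-rank could recover at the same 552 deaths

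*SAP*

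**What the plan says.** SAP 3.1 compares the arms on overall survival with a test that makes no use of baseline information: survival "will be compared using an unadjusted log-rank test". SAP 5 and 8.4.1 and Protocol 10.2.1 and 10.4 agree; Protocol 10.3 names the log-rank test without qualification.

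The design is sized for "one-sided Type I error probability (α) of 0.025, and 80% power" at an improvement "from 4.6 to 6.0 months, hazard ratio 0.767". "A total of 552 deaths will be required to detect the 30% increase in median survival", and the size follows: "With a 2:1 allocation ratio and 5% oversampling, a total of 600 subjects", "with 18 month follow-up of the overall study population". SAP 5.1 places looks at 276, 414 and 552 deaths, with efficacy p-value boundaries of 0.0029, 0.0121 and 0.025 and futility boundaries of 0.25 and 0.08 at the two interims.

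ECOG 0, 1 and 2 are all eligible (Protocol 4.1), and ECOG is a screening procedure (Protocol 5.4 and the study calendar). On allocation, SAP 6 says: "The randomization will not be stratified on any factor". ECOG appears in two supportive analyses in SAP 8.4.1. One is a survival summary by stratum. The other is a Cox model whose covariates, chosen mainly on prior knowledge, include "ECOG performance status (2 categories ECOG 0 and 1 pooled together, and ECOG 2". That model is exploratory and uses backward selection at 0.10, so ECOG may drop out of it. Neither document explains why the primary test omits ECOG, or gives the expected ECOG mix or its effect on survival.

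**The concern.** When patients with different prognoses are pooled, the higher-risk patients die first, and they die faster on control. The arms' risk sets then drift apart in composition, and a hazard ratio that is constant within prognostic groups is pulled toward 1 in the pooled comparison. An unadjusted log-rank test absorbs that dilution. A stratified log-rank test compares patients only within the same ECOG group and avoids it.

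Here the stratifier is already collected and already dichotomised by the sponsor, and neither randomisation nor the primary test uses it. The design has no spare power beyond 80%, so any efficiency available without more patients is worth having.

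**Working it through.** **1. Reproduce the plan's figure.** Exponential hazards from the medians are ln 2/4.6 = 0.151 and ln 2/6.0 = 0.116, with ratio 4.6/6.0 = 0.767. For a fixed design with two thirds of patients on active treatment, Schoenfeld's formula gives

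d = (1.960 + 0.842)² / [(2/3)(1/3)(ln 0.767)²] = 7.849 / (0.2222 × 0.07037) = 502.

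A one-sided O'Brien-Fleming design with efficacy and binding futility boundaries at 50%, 75% and 100% information inflates this by 1.107, to 555 deaths (554 with 4.6/6.0 unrounded). It returns efficacy p-values of 0.0029, 0.0121 and 0.0254 and futility p-values of 0.249 and 0.080, which match SAP 5.1. Power at 552 deaths with the SAP boundaries is 79.7%. The plan's sizing therefore reproduces.

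**2. Compare the two tests under the actual design.** From the documents: 600 patients, 2:1, hazard ratio 0.767, looks at 276, 414 and 552 deaths, SAP 5.1 boundaries, control median 4.6 months over the mixed population. Assumed: ECOG 2 share, hazard ratio for death of ECOG 2 versus 0-1, uniform accrual over 12 months, and 0.767 holding within each ECOG group. There were 4,000 simulated trials per row, so each power has a simulation error of about 0.6 points. Equivalent deaths = 552 × (mean stratified z / mean unadjusted z)², with z taken at 552 deaths.

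| ECOG 2 share | ECOG hazard ratio | Unadjusted power | Stratified power | Gain (points) | Equivalent deaths |
|---|---|---|---|---|---|
| 10% | 1.5 | 79.4% | 80.0% | 0.6 | 558 |
| 10% | 2.0 | 79.0% | 80.5% | 1.5 | 572 |
| 10% | 2.5 | 79.5% | 82.1% | 2.6 | 587 |
| 20% | 1.5 | 79.0% | 80.2% | 1.2 | 568 |
| 20% | 2.0 | 77.6% | 80.3% | 2.7 | 599 |
| 20% | 2.5 | 75.1% | 80.6% | 5.5 | 630 |
| 30% | 1.5 | 77.9% | 79.8% | 1.9 | 576 |
| 30% | 2.0 | 76.1% | 80.6% | 4.5 | 623 |
| 30% | 2.5 | 72.2% | 80.1% | 7.9 | 671 |
| 20% | 1.0 (no effect) | 81.4% | 81.1% | -0.3 | 550 |

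Central case: 552 × (2.945/2.828)² = 599, so the unadjusted test forgoes the equivalent of 599 - 552 = 47 deaths. Accrual over 6 or 18 months gives gains of 2.9 and 3.5 points in that case.

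**3. Check against separate simulations.** A second simulation of the same design gave unadjusted versus stratified power of 80.2 versus 80.7% (15%, 1.5), 77.0 versus 80.3% (20%, 2.0) and 73.5 versus 80.0% (30%, 2.5), and 80.6 versus 80.4% with no ECOG effect. A third, with 3,000 trials per scenario, gave gains of 0.3 points (15%, 1.5; standard error 0.4) and 7.7 points (30%, 2.5). With only 5% ECOG 2 the gain was 0.1 to 0.2 points (standard error 0.3), indistinguishable from zero.

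**4. Type I error.** With no treatment effect (20%, 2.0), rejection rates were 2.8% unadjusted and 2.9% stratified (6,000 trials, simulation error about 0.2 points), and 2.6% versus 2.8% in the second simulation. The tests do not differ beyond simulation error.

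**5. If 0.767 is the whole-population hazard ratio.** The unadjusted test then has its planned 80%. Scaling by the ratio of mean z, stratified power ≈ Φ(2.802 × ratio - 1.960):

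- 10%, 1.5: ratio 2.943/2.926 = 1.006, power about 80.5%.
- 20%, 2.0: ratio 2.945/2.828 = 1.041, power about 83%.
- 30%, 2.5: ratio 2.953/2.679 = 1.102, power about 87%.

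**The case against.** The strongest reply is that nothing is broken. The unadjusted log-rank test controls type I error, is the test for which the trial was sized, and is named consistently. Chance ECOG imbalance is already part of the randomisation distribution that the test's error rate covers. All of this stands.

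A reader might infer that the trial is underpowered or that 552 deaths is wrong. The documents do not support that. The figure reproduces, and 0.767 comes from whole-arm medians, which points to a whole-population effect. On that reading the unadjusted test keeps its planned power, and stratifying adds to it. The unadjusted powers below 80% in the table arise only if 0.767 is taken to hold within ECOG groups.

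The size is also open. ECOG 2 could be uncommon: Protocol 4.1 asks that patients be judged fit to stay on trial for three months, and SAP 8.4.1 allows a covariate to be dropped when one level has too few patients. Being listed as a covariate is not evidence of a strong effect. Age, number of prior regimens, KRAS status and BMI are listed on the same basis, so singling out ECOG is partly a judgement; its advantages are a ready two-level coding and a screening value for every patient.

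These points limit the size and the urgency. They do not show any loss from stratifying: with no ECOG effect the tests perform alike.

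**Conclusion.** The point holds as forgone efficiency in a valid test. Under the SAP's three-look design, with 0.767 within ECOG groups, the gain from stratifying is about 0.5 points (15% ECOG 2, ECOG hazard ratio 1.5), about 3 points (20%, 2.0) and 6 to 8 points (30%, 2.5), and about zero if ECOG 2 is rare or not prognostic. The direction is secure wherever ECOG is prognostic. The size rests on the assumed ECOG share, ECOG hazard ratio and accrual pattern, none of which the documents supply. The change is worth making because it costs little, not because the present plan fails.

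**What to change.** Before any unblinded look, define the primary test at all three analyses as a log-rank test stratified by ECOG at screening (0-1 versus 2), using the last value before randomisation. The definition matters because ECOG is assessed again at Cycle 1 Day 1, which may fall up to 7 days after randomisation. Report the hazard ratio from a Cox model stratified in the same way, and keep the unadjusted log-rank test as a sensitivity analysis. Unstratified randomisation is no obstacle.

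Make the change together in SAP 3.1, 5 and 8.4.1, in Protocol 10.2.1, 10.3 and 10.4, and in the Interim Analysis Plan code, so that no two places name different primary tests. Because the protocol text changes, an approved amendment under Protocol 11.3 is needed, plus minor programming. Patients, deaths, looks and boundaries stay as they are.
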